## APPENDIX B. COVID-19 PANDEMIC MITIGATION STRATEGIES AND INSTRUCTIONS

The COVID-19 global pandemic is an evolving situation and presents numerous challenges to the ongoing conduct of clinical trials. The sponsor has issued the following Protocol considerations to ensure participant safety is maintained and adequate benefit/risk analyses are applied relative to the completion of study procedures and maintaining the investigational product supply chain.

Recognizing the flexibility required to manage the impact of the pandemic on this clinical trial, additional details will be added as needed to respective study manuals and project plan documents and communicated to the investigative sites as needed.

### Number of Study Participants

The evolving situation of the pandemic may result in a substantial number of participants' early dropout from the study, which could affect the data integrity of the trial. Because of this risk and in order to mitigate it, the sponsor may decide to recruit additional participants in the study, beyond the expected number.

### Study Visits

#### Remote Site Visit Guidelines:

In addition to the remote visits already specified in the Protocol, the evolving situation of the pandemic may require further travel restrictions and isolation requirements, or the investigator's benefit/risk assessment may determine it to be unsafe for participants to attend study visits at the investigational site. In such cases, the site staff may elect to pursue the following:

- In order to minimize participant risk, study visits may be conducted via telemedicine modalities (phone or video calls). At a minimum, a review of AEs, concomitant medications, and study drug compliance must be completed. Periodic on-site visits should be conducted whenever feasible, in addition to the mandatory on-site visits outlined below.
- No efficacy assessments can be performed via telemedicine (video call or phone call).
- Laboratory sampling: in order to support investigator oversight of participant safety and disease management, off-site laboratory sampling (in accordance with the SoA, see [Table 3](#)) may be allowed in 1 of 2 ways:
  - Use of home nursing services.
  - Instruct the participant to undergo some laboratory tests at a local (nearby) hospital laboratory or facility closer to the participant's residence rather than at the investigational site. In this case, the study physician will provide the participant with the list of parameters to be checked. These tests should be performed at certified laboratories and copies of results provided to the site.

### **Mandatory On-Site Visits:**

The visits outlined below **must be performed in person** in order to capture the investigator's efficacy assessments and the patient-reported outcomes, even if the date that the participant eventually comes into the clinic deviates from the visit window.

No efficacy assessments can be performed via telemedicine (video call, phone call, or photography).

The visit window deviation must be documented, and the sponsor's representative must be informed of when it is believed that the participant can come into the clinic. Further instructions will be provided if needed.

During the DBVC period, the following visits must be performed in person:

- Screening
- Day 1 (baseline)
- Week 16 visit

During the OLE period, the following visits must be performed in person:

- Week 32 visit

### **Investigational Medicinal Product Dispensing and Distribution**

In order to ensure the continuity of providing their participants' clinical supplies within the constraints imparted by the pandemic, the site staff can decide to supply study drug via shipment to participants.

If the participant cannot attend a visit at the study site, adequate supplies of study drug determined by the investigator can be shipped to the participant by the investigator or appropriately delegated staff (eg, the study pharmacy staff) using a third-party service if duly authorized by the participant.

The study site may use their own preferred courier, provided the courier adheres to certain standards (eg, use of personal protection equipment, maintenance of temperature-controlled transit environment), or one centrally contracted by the sponsor.

### **Clinical Trial Monitoring**

Study monitoring visits may be postponed due to documented COVID-19-related reasons; however, the site monitor will continue to employ off-site monitoring practices such as routine communication methods (eg, phone calls, e-mails, video visits) with the sites to get information on trial progress, participant status, and information on issue resolution. The study monitor may remotely review data entered into the EDC for accuracy and completeness. If allowed by local regulations, remote source data verification may be implemented with agreement of the principal investigator and institution, as applicable.

If the study-site monitor cannot be on-site to perform the final drug accountability for reconciliation purposes and the operation cannot be postponed, it may be performed by a pharmacist from the hospital pharmacy or by the study coordinator/data manager with suitable

training. The study drug can be returned to the sponsor by the hospital pharmacy directly or destroyed in accordance with local practices, if applicable, and with sponsor approval.

## **Other Considerations**

If necessary, direct contracts can be established with third-party local physicians to conduct activities related to the clinical management of participants for whom the investigator is responsible and maintains oversight. In such situations, the investigator is required to provide the local physician with a delegation letter listing all delegated activities. The sponsor, through the study investigator or institution, will reimburse the local physician for the tests/procedures conducted outside of the standard of care.

- In case of need, participants may refer to the local health care provider. Participants will be requested to obtain certified copies of the source data at the local health facility with the outcome of the contact and provide those to the investigator for appropriate oversight. The investigator/delegate will be requested to enter any relevant information into the EDC.
- Should COVID-19-related restrictions be localized and have an effect on a limited number of sites, the affected sites may utilize direct contracting of third parties to support continuous study conduct (eg, home nursing services, couriers, etc).

## **Reimbursement of Extraordinary Expenses**

The sponsor will arrange to reimburse participants for any extraordinary expenses, keeping appropriate documentation as evidence (eg, travel expenses for the local laboratory visit[s], the costs of local [nearby] laboratory tests).

1. INTRODUCTION

INCB 18424-221 is a Phase 2, randomized, DBVC, efficacy, and safety study in participants aged \geq 18 years with a diagnosis of HS. The study will consist of a 16-week DBVC period followed by a 16-week OLE period. A 30-day post-treatment safety follow-up visit will be conducted after the OLE period.

The purpose of this SAP is to provide details of the statistical analyses that have been outlined in the INCB 18424-221 Protocol.

2. STUDY INFORMATION, OBJECTIVES, AND ENDPOINTS

2.1. Protocol and Case Report Form Version

This SAP is based on INCB 18424-221 Protocol dated 19 AUG 2022 and CRFs approved 14 AUG 2023. Unless superseded by an amendment, this SAP will be effective for all subsequent Protocol amendments and eCRF versions.

2.2. Study Objectives and Endpoints

[Table 1](#) presents the objectives and endpoints.

Table 1: Objectives and Endpoints

Objectives	Endpoints
Primary	
To establish the efficacy of ruxolitinib 1.5% cream BID in participants with HS.	Change from baseline in AN count at Week 16.
Secondary	
To further evaluate the treatment effect of ruxolitinib 1.5% cream BID in participants with HS.	
Change from baseline to Week 16 in total AN count in anatomical areas with pre-existing AN at baseline. Note: Pre-existing AN at baseline are defined as abscesses and/or inflammatory nodules present at baseline.Proportion of participants achieving AN50, AN75, AN90, and AN100 (at least 50%, 75%, 90%, and 100% reduction, respectively, in AN count relative to baseline) at Week 16.Change from baseline in the Skin Pain NRS score at Week 16.Change from baseline in the Itch NRS score at Week 16.Proportion of participants who achieve HiSCR at Week 16. Note: HiSCR is defined as at least 50% reduction in AN count with no increase in either abscess or draining fistula counts, relative to baseline.Change from baseline in the IHS4 score at Week 16.Note: IHS4 score is calculated by the number of inflammatory nodules (multiplied by 1) plus the number of abscesses (multiplied by 2) plus the number of draining tunnels (multiplied by 4).
To evaluate the safety and tolerability of ruxolitinib 1.5% cream BID in participants with HS.	The type, frequency, and severity of AEs, and changes in vital signs and hematology and serum chemistry parameters.

Table 1: Objectives and Endpoints (Continued)

[figure not shown]
3. STUDY DESIGN

This is a Phase 2, randomized, DBVC study in participants aged ≥ 18 years with confirmed diagnosis of HS. The study will consist of a 16-week DBVC period followed by a 16-week OLE period.

Participants will be screened for up to 28 days prior to the first application of ruxolitinib 1.5% cream or vehicle cream. Approximately 60 eligible participants aged ≥ 18 years will be randomized 1:1 to either ruxolitinib 1.5% cream or vehicle cream. Participants will be stratified by baseline AN count (ie, ≥ 3 to 4 or ≥ 5 to 10). Participants will apply either ruxolitinib 1.5% cream BID or vehicle cream BID through Week 16 to all affected areas identified at baseline. At Week 16, participants who meet the criteria (compliant with the Protocol and without safety concerns) will enter the 16-week OLE period. Participants randomized to vehicle BID in the DBVC period will be crossed over to ruxolitinib 1.5% cream BID and participants randomized to ruxolitinib 1.5% cream BID at baseline will remain on ruxolitinib 1.5% cream BID through Week 32 in an open-label fashion. Participants will enter the 30-day safety follow-up period after the last application of study treatment.

The study schema is shown below in [Figure 1](#).

Figure 1: Study Design Schema

Abbreviations: Rux = ruxolitinib.

The primary analysis will occur after the primary database lock, when all participants have completed or discontinued from the DBVC period. The final analysis will occur when all participants have completed or withdrawn from the study, whichever comes first.

3.1. Randomization

Approximately 60 participants will be randomized 1:1 to either ruxolitinib 1.5% cream BID or vehicle cream. Participants will be stratified by baseline AN count (ie, ≥ 3 to 4 or ≥ 5 to 10).

3.2. Control of Type I Error

The significance level for primary efficacy analysis will be 0.1 for a 2-sided test.

3.3. Sample Size Considerations

Approximately 60 participants will be randomized 1:1 to ruxolitinib 1.5% cream BID or vehicle BID. The sample size was not calculated based on statistical power calculations, but for demonstration of preliminary findings of clinical response. It is anticipated that a sample size of approximately 60 participants will 1) generate sufficient data to assess whether ruxolitinib 1.5% cream warrants further investigation in HS, and 2) be sufficient to provide enough data for an initial evaluation of the safety profile of ruxolitinib 1.5% cream in HS.

3.4. Schedule of Assessments

Refer to Protocol dated 19 AUG 2022 for a full description of all study procedures and assessment schedules for this study.

4. DATA HANDLING DEFINITIONS AND CONVENTIONS

4.1. Scheduled Study Evaluations and Study Periods

4.1.1. Day 1

Day 1 is the date that the first application of ruxolitinib 1.5% cream or vehicle cream is administered to the participants in the specific period.

For randomized participants not treated with any study drug, Day 1 is defined as the date of randomization.

4.1.3. Baseline Value

For the DBVC period, baseline is the last nonmissing measurement obtained before or on the day of the first application of ruxolitinib 1.5% cream or vehicle cream in the DBVC period, unless otherwise defined.

For randomized participants not treated with any study drug, baseline is defined as the last nonmissing assessment before or on the date of randomization.

For participants who continue in the OLE period, baseline is defined as follows:

- For efficacy evaluation in the OLE period, baseline is the last nonmissing measurement obtained before or on the day of first application of study treatment in the DBVC period.
- For safety evaluation in the OLE period, baseline is the last nonmissing measurement obtained before or on the day of first application of ruxolitinib 1.5% cream in the study.

When a scheduled assessment and an unscheduled assessment occur on the same day and the times of the assessments are not available, use the following convention to determine baseline:

- If both a scheduled and an unscheduled visit are available on the day of the first application and the time is missing, use the scheduled assessment as baseline.
- If the scheduled assessment is missing on the day of the first application and an unscheduled assessment is available, use the unscheduled assessment as baseline.

4.1.4. Handling of Missing and Incomplete Dates

In general, values for missing dates will not be handled unless methods for handling missing dates are specified in this section or relevant sections. The original reported dates collected on the eCRF should be used in all relevant listings. The following rules will be used for handling partial dates for analyses requiring dates.

Partial HS diagnosis date will be handled, as follows, in the calculation:

- If only the day is missing, then the first day of the month will be used.
- If both the month and day are missing, then 01 JAN of the year will be used.
- If the diagnosis date is completely missing, then the time since diagnosis will not be calculated.

When the date of the last application is used in deriving variables, such as duration of treatment or TEAE flag, a missing date of the last application in the specified treatment period will be handled as follows:

- If the last application date is missing, then the end date of the specified treatment period will be used as the date of the last application.
- If the last application date and the end date of the specified treatment period are both missing and the participant is lost to follow-up, then the date of last contact will be used as the date of the last application.

4.2. Variable Definitions

4.2.1. Body Mass Index

Body mass index will be calculated as follows:

$$\text{BMI (kg/m}^2\text{)} = [\text{weight (kg)}] / [\text{height (m)}]^2$$

4.2.2. Prior and Concomitant Medications

A prior medication is defined as any nonstudy medication started before the first application of ruxolitinib 1.5% cream or vehicle cream.

A concomitant medication is defined as any nonstudy medication that is started accordingly:

- Before the date of first application of ruxolitinib 1.5% cream or vehicle cream and is ongoing throughout the study or ends on/after the date of first study drug application.
- On/after the date of first application of ruxolitinib 1.5% cream or vehicle cream and is ongoing or ends during the course of the study.

A prior medication could also be classified as "both prior and concomitant medication" if the end date is on or after first application of ruxolitinib 1.5% cream or vehicle cream. In the listing, it will be indicated whether a medication is only prior, only concomitant, or both prior and concomitant.

For the purposes of analysis, all medications will be considered concomitant medications unless the medications can unequivocally be defined as not concomitant.

5. STATISTICAL METHODOLOGY

5.1. General Methodology

Unless otherwise noted, SAS® software (SAS Institute Inc, Cary, NC; v9.4 or later) will be used for the generation of all tables, graphs, and statistical analyses. Descriptive summaries for continuous variables will include, but not be limited to, the number of observations, mean, standard deviation, median, minimum, and maximum. Descriptive summaries for categorical variables will include the number and percentage of participants in each category.

5.2. Treatment Groups

This is a randomized study with DBVC and OLE periods.

Efficacy data will be presented by treatment group assigned at study entry for the ITT population. The treatment groups will be 1.5% BID (ie, ruxolitinib 1.5% cream BID) and vehicle BID.

Safety data will be presented by treatment group that participants actually applied.

- For safety data in the DBVC period, the treatment groups will be 1.5% BID and vehicle BID.
- For safety data in the OLE period, the treatment groups will be 1.5% BID to 1.5% BID and vehicle BID to 1.5% BID.
- For safety data throughout the study, the only treatment group will be 1.5% BID, including participants who applied ruxolitinib 1.5% cream BID from Day 1 through Week 32 or end of study treatment.

5.3. Analysis Populations

5.3.1. Intent-to-Treat Population

All participants who are randomized will constitute the ITT population. Treatment groups for this population will be defined according to the treatment assignment at the time of randomization regardless of the actual study drug the participant might take during their participation in the DBVC period.

The ITT population will be used for the summary of demographics, baseline characteristics, participant disposition, medical history, prior and concomitant medications, and analyses of all efficacy data, unless otherwise specified.

5.3.2. Safety Population

The safety population will include all participants who applied ruxolitinib 1.5% cream or vehicle cream at least once. Treatment groups for this population will be determined according to the actual treatment the participant applied on Day 1 regardless of assigned treatment group.

The safety population will be used for safety summaries in the DBVC period.

5.3.2.1. Open-Label Extension Safety Population

The OLE safety population includes all participants who applied ruxolitinib 1.5% cream BID at least once during the OLE period.

All safety analyses conducted specifically for the OLE period will use the OLE safety population.

[REDACTED]

6. BASELINE, EXPOSURE, AND DISPOSITION

[Appendix A](#) provides a list of planned tables, figures, and listings. Sample data displays are included in a separate document.

6.1. Demographics, Baseline Characteristics, and Disease History

6.1.1. Demographics and Baseline Characteristics

The following demographics and baseline characteristics will be summarized by treatment group and overall for the ITT population in the DBVC period and for the OLE safety population in the OLE period: age, sex, race, ethnicity, weight, height, and BMI.

6.1.2. Baseline Disease Characteristics

For the ITT population, the baseline disease characteristics will be summarized and analyzed by treatment group and will include, but not be limited to the following:

- Disease duration (months)
- Prior surgical treatment for HS (yes [incision and drainage, deroofing, or other]/no)
- Prior therapy received for HS
- HS family history (yes/no)
- Selected comorbidities
- Number of anatomical areas with HS
- Days since onset of current episode of HS flare/activity
- Number of HS flares since diagnosis
- Hurley stage
- AN count category (≥ 3 to 4 or ≥ 5 to 10)
- AN count
- Inflammatory nodule count
- Abscess count
- Nondraining tunnel count
- Draining tunnel count
- Skin Pain NRS score
- Itch NRS score
- Total BSA involvement

6.1.3. Disease History

The time since diagnosis will be summarized for all participants in the ITT population.

Time since diagnosis will be calculated as follows:

Disease duration (months) = (date of randomization – date of initial HS diagnosis +1) / 30.4375.

6.1.4. Medical History

For participants in the ITT population during the DBVC period, medical history will be summarized by assigned treatment groups. This summary will include the number and percentage of participants with medical history for each body system/organ class as documented on the eCRF.

6.2. Disposition of Participant

The number and percentage of participants who were randomized, treated, and completed the DBVC period, as well as the number and percentage of participants who discontinued the treatment or withdrew from the study during the DBVC period with a primary reason for discontinuation, will be summarized for the ITT population.

The number and percentage of participants who completed the OLE period, in addition to those participants who discontinued treatment or withdrew from the study during the OLE period with a primary reason for discontinuation, will be summarized for the OLE safety population.

6.3. Protocol Deviations

For participants in the ITT population in the DBVC period, as well as the OLE safety population in the OLE period, Protocol deviations recorded on the eCRF will be summarized and listed by category (critical, major, or minor) for each treatment group and overall.

[REDACTED]

6.6. Prior and Concomitant Medications

Prior medications and concomitant medications will be coded using the WHO Drug Dictionary. The number and percentage of participants with prior and concomitant medications will be summarized by treatment group and overall for the ITT population during the DBVC period by WHO drug class and the WHO drug preferred term. For the OLE period, only concomitant medications will be summarized based on OLE safety population.

7. EFFICACY

[Appendix A](#) provides a list of data displays. Sample data displays are included in a separate document.

7.1. Efficacy Hypothesis

The primary hypothesis is that ruxolitinib 1.5% cream BID, compared with vehicle cream BID, will improve change in AN count from baseline to Week 16 in participants with HS.

7.2. Efficacy Measures

7.2.1. Lesion Counts

The HS lesion counts will be assessed at each study visit by the investigator and used for calculation of efficacy parameters as follows: AN counts, HiSCR, IHS4, and flare incidence.

Lesion count and assessment will be recorded in the lesion count worksheet; the assessment of anatomical regions includes, but is not limited to the left and right axilla and the left and right inguinocrural fold or inframammary areas.

7.2.1.1. Abscess and Inflammatory Nodule Counts

The AN counts will be recorded at all visits. The AN results will be used to calculate change in AN count relative to baseline, as well as AN50, AN75, AN90, and AN100, which are defined as, at least, a 50%, 75%, 90%, and 100% decrease, respectively, in AN count relative to baseline.

7.2.1.2. Hidradenitis Suppurativa Clinical Response

The HiSCR was originally developed based on the underlying Phase 2 trial of adalimumab and validated against meaningful changes in pain score and DLQI ([Kimball et al 2016, Sabat et al 2020](#)). The achievement of HiSCR is defined as at least 50% reduction in AN count with no increase in either abscess or draining fistula counts, relative to baseline. In this study, participants with draining fistulas (tunnels) will be excluded from the study. Should a randomized participant develop a draining tunnel during the study, the participant will be discontinued from the study.

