## 5.2. Exclusion Criteria

Participants are excluded from the study if any of the following criteria apply:

1. Presence of draining tunnels at screening or at baseline visits.
2. Total HS BSA affected (excluding scalp) is  $> 20\%$ .
3. Participants with concurrent conditions and history of other diseases:
  - a. Active ongoing inflammatory diseases of the skin other than HS that might confound the evaluation of HS.
  - b. Any other concomitant skin disorder (eg, generalized erythroderma such as Netherton's syndrome), pigmentation, or extensive scarring that in the opinion of the investigator may interfere with the evaluation of HS AN or compromise participant safety.
  - c. Active tuberculosis; or current and/or history of latent tuberculosis unless adequately treated.
  - d. Immunocompromised (eg, lymphoma, acquired immunodeficiency syndrome, or Wiskott-Aldrich syndrome).
  - e. Chronic or acute infection requiring treatment with systemic antibiotics, antivirals, antiparasitics, antiprotozoals, or antifungals within 2 weeks before baseline.

- f. Active acute bacterial, fungal, or viral skin infection (eg, herpes simplex, herpes zoster, chicken pox, clinically infected AD, or impetigo) within 2 weeks before baseline.
    - g. Unstable asthma or COPD requiring systemic treatment (such as intravenous steroids) or hospital admission or emergency room treatment within 3 months from baseline; or stable asthma or COPD requiring more than 720 µg/day (2 puff BID of 180-ug dose) or fluticasone more than 440 µg/day (2 puffs BID of 110-ug dose) or other equivalent inhaled corticosteroids.
  4. Any serious illness or medical, physical, or psychiatric condition(s) that, in the investigator's opinion, would interfere with full participation in the study, including administration of study drug and attending required study visits; pose a significant risk to the participant; or interfere with interpretation of study data. For example:
    - a. Clinically significant or uncontrolled cardiovascular disease, including unstable angina, acute myocardial infarction, or stroke within 6 months from Day 1 of study drug application, New York Heart Association Class III or IV congestive heart failure, and arrhythmia requiring therapy or persistent uncontrolled hypertension (blood pressure > 150/90 mmHg) unless approved by medical monitor/sponsor.

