## 7. DISCONTINUATION OF STUDY TREATMENT AND PARTICIPANT WITHDRAWAL

### 7.1. Discontinuation of Study Treatment

#### 7.1.1. Reasons for Discontinuation

Participants **must** be discontinued from study treatment for the following reasons:

- Disease worsens during either the DBVC period or the OLE period, to the point where the extent of the affected area to be treated exceeds 20% BSA or there is a draining tunnel(s).
- Worsening HS and treatment with a prohibited medication and/or procedure as noted in Section [6.6.3](#).
- The participant becomes pregnant.
- Consent is withdrawn.

Note: Consent withdrawn means that the participant has explicitly indicated that they do not want to be followed any longer; in this case, no further data, except data in the public domain, may be collected or solicited from the participant. Participants may choose to discontinue study treatment and remain in the study to be followed for progression and survival.

- Further participation would be injurious to the participant's health or well-being, in the investigator's medical judgment.
- Unacceptable toxicity occurs (see Section [6.5.2](#)).
- The study is terminated by the sponsor.
- The study is terminated by the local health authority, IRB, or IEC.

A participant **may** be discontinued from study treatment as follows:

- If, after 2 consecutive study visits and reinforcement of study drug application by site staff, a participant who again fails to meet compliance benchmarks at a subsequent visit may be considered for withdrawal from the study. The medical monitor should be consulted for instruction on handling the participant.
- If, during the course of the study, a participant is found not to have met eligibility criteria at the time of enrollment, the medical monitor, in collaboration with the investigator, will determine whether the participant should be withdrawn from study treatment.
- If a participant is noncompliant with study procedures or study drug application in the investigator's opinion, the sponsor should be consulted for instruction on handling the participant.

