7.2.1.3. International Hidradenitis Suppurativa Severity Score System

The IHS4 ([Zouboulis et al 2017](#)) is a composite, dynamic score, and validated tool, used to determine HS severity. It employs a weighted scale using the number of inflammatory nodules, the number of abscesses, and the number of draining tunnels (eg, fistulas or sinuses), with respective weight factors of 1, 2, and 4. For example, IHS4 score equals the number of inflammatory nodules (multiplied by 1) plus the number of abscesses (multiplied by 2) plus the number of draining tunnels (multiplied by 4).

[REDACTED]

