7.4. Analysis of the Secondary Efficacy Parameters

All secondary efficacy analyses will be conducted for the ITT population.

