7.4.1. Continuous Efficacy Endpoints

The summary and analysis of statistics for the following continuous measurements, including change from baseline, will be presented for each treatment group:

- Total AN count in anatomical areas with pre-existing AN at Week 16
- By-visit Skin Pain NRS score at Week 16
- By-visit Itch NRS score at Week 16
- IHS4 score at Week 16

[figure not shown]
The summary statistics include sample size, mean, median, standard deviation, minimum, maximum, first quartile, third quartile, and 95% confidence interval. A similar MMRM, as specified in the primary efficacy analysis, may be fit for the comparison between ruxolitinib 1.5% cream and vehicle cream at Week 16.

For the endpoint change from baseline in total AN count in anatomical areas with pre-existing AN (ie, not including new AN identified after baseline), only the anatomical areas with an AN count > 0 will be considered for each participant. At baseline, the anatomical areas with abscesses and/or inflammatory nodules will be identified and AN counts in these areas will be summed. At each postbaseline visit, the sum of AN counts in only the pre-existing areas (that were identified at baseline) will be used to calculate the change relative to baseline.

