7.4.2. Categorical Efficacy Endpoints

For the following categorical parameters, summary statistics, including sample size, frequency, and percentages will be presented.

- Proportion of participants achieving AN50/75/90/100 at Week 16
- Proportion of participants achieving HiSCR at Week 16

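### Does the plan leave participants who develop a draining tunnel uncounted in HiSCR and IHS4?

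*SAP*

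**What the plan says.** Entry is closed to anyone with a draining tunnel: Protocol section 5.2 lists "Presence of draining tunnels at screening or at baseline visits" as an exclusion, and inclusion criterion 4 in section 5.1 repeats the requirement. Every eligible participant therefore starts with a tunnel count of zero.

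SAP section 7.2.1.2 defines HiSCR as "at least 50% reduction in AN count with no increase in either abscess or draining fistula counts, relative to baseline". SAP section 7.2.1.3 builds IHS4 from nodules, abscesses and the "number of draining tunnels (eg, fistulas or sinuses), with respective weight factors of 1, 2, and 4". Directly after the HiSCR definition, SAP section 7.2.1.2 states: "Should a randomized participant develop a draining tunnel during the study, the participant will be discontinued from the study". Protocol section 8.2.1.2 says the same. Protocol section 7.1.1 lists a draining tunnel among the reasons for mandatory discontinuation of study treatment.

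On analysis, SAP section 7.4 says: "All secondary efficacy analyses will be conducted for the ITT population". For HiSCR and AN50 to AN100, section 7.4.2 says: "For the following categorical parameters, summary statistics, including sample size, frequency, and percentages will be presented". For IHS4, section 7.4.1 gives summary statistics and adds: "A similar MMRM, as specified in the primary efficacy analysis, may be fit for the comparison between ruxolitinib 1.5% cream and vehicle cream". The statement that participants with missing Week 16 data are included belongs to the primary analysis (SAP section 7.3.1).

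**The concern.** With a baseline of zero, any new draining tunnel is an automatic HiSCR failure and adds 4 points to IHS4. The same tunnel takes the participant out. A score that goes missing because one of its own components got worse is informatively missing, and the readable sections do not say what value or response status these participants receive.

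If the count taken at exit is not used as Week 16, the tunnel term can score only when the tunnel is first seen at the Week 16 visit itself. The observed Week 16 IHS4 mean then omits those who worsened this way, so the arm with more tunnels looks better than it was. The optional MMRM would treat the exits as missing at random, which is doubtful for an exit of this kind. For HiSCR, leaving exits out of the denominator would raise the response rate in the arm that lost more people. The difference between discontinuing study treatment and discontinuing the study also seems to bear on whether a Week 16 count exists.

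**Working it through.** There is no plan figure to reproduce. About 60 participants are randomized 1:1, the size is stated not to rest on power (SAP section 3.3), and neither endpoint has a design assumption. The documents give no tunnel incidence, so the inputs marked as assumed are illustrative.

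**1. How often the tunnel term could score at Week 16.** The lesion-count visits after baseline are Weeks 2, 4, 8, 12 and 16. With constant onset over 16 weeks (assumed), the share of new tunnels first seen at Week 16 is (16 − 12)/16 = 25%. For an assumed 16-week incidence of 5%, 10% or 15% in 60 participants:

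| Incidence | New tunnels | Seen before Week 16 | First seen at Week 16 |
|---|---|---|---|
| 5% | 3 | 2.25 | 0.75 |
| 10% | 6 | 4.5 | 1.5 |
| 15% | 9 | 6.75 | 2.25 |

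The tunnel term is nearly empty only if exit counts are not mapped to Week 16. If they are mapped, all 3, 6 or 9 tunnels score, provided the exit visit takes place.

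**2. HiSCR.** Two treatments of a tunnel exit fit the ITT label. If the exit count is used, the tunnel count has risen from zero and HiSCR fails by definition. If Week 16 is missing, the participant stays in the all-randomized denominator and is not among the achievers. Both give non-response. Only an observed-case denominator differs. To size that, take 13/30 and 8/30 responders, which are the rounded values of 42% and 26% × 30 (the rates that Protocol section 2.1 cites for adalimumab in moderate-to-severe disease; borrowed, not expected here).

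- All randomized: 13/30 − 8/30 = 43.3% − 26.7% = 16.7 points. SE = √(0.433 × 0.567/30 + 0.267 × 0.733/30) = 12.1 points.
- Three vehicle exits dropped: 13/30 − 8/27 = 13.7 points.
- One active exit dropped: 13/29 − 8/30 = 18.2 points.
- Five vehicle exits dropped: 13/30 − 8/25 = 11.3 points.

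**3. IHS4.** An AN count of 3 to 10 gives a baseline IHS4 from 3 (three nodules) to 20 (ten abscesses), so one tunnel is 4/20 = 20% to 4/3 = 133% of a baseline score. Let k of 30 in one arm leave with one tunnel and unchanged nodules and abscesses (change +4), while the others average m. Omitting the exits makes that arm's mean look better by k(4 − m)/30.

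- m = −2: 0.20, 0.40 and 0.60 for k = 1, 2 and 3.
- m = −1: 0.17 to 0.50. m = −3: 0.23 to 0.70.
- SE of the arm difference = SD × √(2/30) = 0.77, 1.03 and 1.29 for an assumed SD of 3, 4 and 5.

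The largest ratio for up to three exits is 0.70/0.77 = 0.91 of one SE. Five exits in one arm and none in the other, with m = −2, give 5 × 6/30 = 1.0 point, or 0.8 to 1.3 SE.

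**4. What is recorded anyway.** Protocol section 7.1.2 calls for an early-termination visit on permanent discontinuation. Table 3 of the Protocol places Week 16 and that visit (ET1) in one column with a lesion count. SAP section 6.2 tabulates discontinuations by primary reason, HiSCR and IHS4 are tabulated over the study period (Tables 2.4.1 and 2.5.1), and lesion counts are listed (Listing 2.6.1.1).

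**The case for a change.** The strongest case for a change is that an ITT label says who is analyzed, not what value they take. For IHS4 that is right: a mean needs a number. Under Protocol section 8.7 the early-termination assessment replaces a coinciding scheduled visit and goes on its own form page, so two programmers could reach different Week 16 IHS4 summaries from the same data. One or two sentences would prevent that, at almost no cost.

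This part stands: the readable SAP does not state how the ET1 count enters IHS4. It is a missing detail, though, not a rule that gives a wrong answer. SAP numbering passes from 4.1.1 to 4.1.3 in the public copy, under a heading on scheduled evaluations and study periods where a visit-mapping rule could sit, and the table shells are also separate. Text withheld in this way cannot be counted as absent from the plan.

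The rest is weaker. The wordings about leaving study treatment and leaving the study do differ, and those passages must be reconciled; this note does not say which is right. Yet both lead to an early-termination visit and then safety follow-up (Protocol sections 7.1.2 and 8.8.1), and the schedule has no separate off-treatment efficacy visits. The remark in Protocol section 7.1.1 about staying in the study after stopping treatment sits under withdrawal of consent, not under tunnels. Progression of mild disease is mentioned in Protocol section 2.1 as an unmet need; section 2.2 gives the purpose as assessing efficacy and safety, and no readable endpoint is tunnel progression.

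**Conclusion.** No change to the plan is needed. The structural observation is correct: a new tunnel worsens both scores and also ends participation. For HiSCR, the ITT population already makes these participants non-achievers under either sensible handling. For IHS4, analysts have an exit count to use, or a missing value to report beside a disposition table that gives reasons for discontinuation. How finely those reasons identify tunnels is not shown, but the lesion listing would show them.

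For one to three one-sided exits per 30, the IHS4 shift is 0.17 to 0.70 points, always below one assumed SE. HiSCR moves by about 3 points at most against an SE of about 12, and only if exits are dropped contrary to the ITT label. The IHS4 shift reaches one SE only in a lopsided case such as five exits to none with a small SD, which would be plain in the disposition table. These sizes rest on assumed exit counts, mean changes, SDs and borrowed response rates. HiSCR and IHS4 are secondary and mainly descriptive, the significance level in SAP section 3.2 applies to the primary analysis only, and this point does not challenge the primary AN analysis.
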